With funding from a Career Development Award from the Veteran's Affairs (VA) and rigorous formative research, we developed a technology-assisted weight management intervention, called Goals for Eating and Moving (GEM). This intervention is based on the 5As framework (assess, advise, agree, assist, arrange) as recommended by the United States Preventive Services Task Force and reimbursed by the Centers for Medicare and Medicaid Services. The GEM intervention uses a tablet-delivered online tool to facilitate in-person and telephone-delivered health coaching by non-clinical staff, provide tailored patient education materials, and activate patients to set behavior change goals and discuss weight management treatments with their healthcare teams. Preliminary data suggests that the GEM intervention is feasible and acceptable to Veterans and VA staff and facilitates 5As counseling. An ongoing RCT will determine if it promotes weight loss.

The Patient-Centered Medical Home model is an expanded care model emphasizing patient-centered care delivered by inter-professional teams of individuals working to integrate evidence based approaches to improve individual and population health.^{14,15} However, it is unclear how the Patient-Centered Medical Home model can be used to address barriers to 5As implementation, improve weight management counseling, and increase participation in intensive weight management programs. We developed GEM (Goals for Eating and Moving), an innovative, technology-assisted 5As-based intervention for Medical Homes to promote weight loss, behavior change, and participation in intensive weight management programs. To establish the efficacy of the GEM intervention, we will conduct a cluster randomized controlled 12-month intervention of 16 primary care teams at two urban healthcare systems with Medical Home models of care to compare the GEM intervention (intervention arm) with Enhanced Usual Care (educational materials; control arm).

Specific Aims

1. Test the impact of the GEM intervention on weight change, and clinical and behavioral outcomes.
2. Identify predictors of weight loss in the GEM intervention arm related to: a) goal-setting processes and b) intervention components
3. Determine the impact of the GEM intervention on obesity-related counseling practices and attitudes in primary care providers.

Hypothesis

The patients within primary care teams randomized to the Goals for Eating and Moving (GEM) intervention will have greater weight loss than those who receive Enhanced Usual Care.

Research Design

- a. We will conduct a cluster-randomized controlled trial of the GEM intervention at two healthcare systems in New York City: The VA New York Harbor Healthcare System (Manhattan campus) and Montefiore Medical Groups (4 sites affiliated with New York City Research and Improvement Networking practice-based research network).
- b. We will conduct a RE-AIM (reach, efficacy, adoption, implementation, and maintenance) evaluation of the GEM intervention.²⁰
- c. We will explore potential effects of secondary measures such as perceived procedural fairness or experiences of discrimination on health outcomes and weight-loss behaviors including but not limited to dietary behaviors, physical activity, and quality of life measures.

Background

Modest weight loss (7%) via the Diabetes Prevention Program (DPP) can reduce the risk of diabetes in high-risk patients by 58%.³ Similarly, all Veterans Affairs (VA) Medical Centers offer the MOVE! program, a lifestyle-based program delivered in small group sessions.^{4, 26, 27} One report found that patients who attended two or more MOVE! sessions were more likely than matched controls to have clinically significant (>5%) weight loss and less likely to gain weight.²⁸ Unfortunately, intensive lifestyle programs like this are not available to most primary care patients and very few studies have looked at interventions to treat obesity in the primary care setting,²⁹⁻³⁰ despite the obvious need for improving delivery of obesity care. We need to test more robust strategies to increase participation in these effective programs.

The primary care setting is critical to reducing the burden of obesity. Primary care (PC) is an important venue to promote weight loss through lifestyle behavior change, and effective PC-based interventions can potentially have a significant public health impact,

since the majority of the 1 billion yearly ambulatory visits are made to primary care physicians.⁹ Moreover, physicians' and other providers' counseling is associated with positive behavioral and weight-loss outcomes.³¹⁻³⁴ The United States Preventive Services Task Force endorses the use of the 5As framework (Assess, Advise, Agree, Assist, Arrange) to deliver obesity counseling within primary care.³⁵ While Medicare reimburses providers for 5As weight management counseling, providers frequently fail to effectively counsel obese patients to lose weight.^{33, 36} This has been attributed to lack of training,^{34,37} poor competency,³⁸ perceived lack of effectiveness,³⁹ and competing demands on time during the medical visit.⁴⁰ Thus, more studies are needed to determine the best way to integrate weight management into primary care practice.

With funding from a Career Development Award (CDA) from the Veterans Affairs, we recently developed a technology-assisted, weight management intervention called Goals for Eating and Moving (GEM) to deliver 5As weight management counseling within a patient centered medical home model of care (PCMH). Figure 1 illustrates how the intervention is delivered within PCMH and promotes goal setting and weight loss. Patients arrive early to their PC appointment to use an online goal setting tool (GEM tool) delivered on a tablet computer that generates a personalized binder of tailored materials. The patient then meets with a health coach to further refine weight loss and lifestyle goals, address barriers, and suggest other weight management resources. PC teams then endorse goals and provide brief motivational interviewing as needed. They can use a clinical reminder within the electronic health record to document 5As counseling conversations. Patients receive follow-up phone coaching calls from their health coach to document progress, adjust goals, and facilitate communication with the health care team and weight management-related services.

The GEM intervention has great potential to improve the delivery of obesity counseling within the PCMH model of primary care. Initial findings from an ongoing pilot study of this intervention among Veterans and PC staff at a VA medical center demonstrated that it was feasible and acceptable to Veterans and staff and facilitated goal-setting conversations (see Preliminary Studies). However, there is no standard by which to leverage the Patient-Centered Medical Home model to provide weight management care. There is a need to test weight management interventions within patient-centered medical homes that integrate and/or partner with effective, intensive programs such as MOVE! and DPP.

[name] (Co-I) has over three decades of experience leading multicenter and investigator-initiated lifestyle trials for diet, obesity, and exercise whose work in Diabetes Prevention Program (DPP), DDP-Outcomes Study and Women's Health Initiative has shaped national health guidelines.⁵²⁻⁵⁶

Study Design

We will conduct this study using 3 steps:

1. Test the impact of the GEM Intervention on weight change, and clinical and behavioral outcomes.
 - a. We will obtain weight and height measurements, waist circumference measurements, , and blood pressure measurements from patients at multiple time points throughout the study. We will also use questionnaires to measure dietary outcomes and physical activity outcomes. Finally, electronic health records (EHR) and surveys will be utilized to evaluate attendance to intensive weight management programs. ^{85, 96, 86, 97, 98, 99, 100, 101, 102}
2. Identify predictors of weight loss in the GEM intervention arm related to: a) goal-setting processes and b) intervention components.
 - a. We will measure attainment of behavioral goals by asking patients to report on how many days in the past week they achieved each of their SMART goals. ⁸⁸ We will record the number of telephone coaching calls received by patients within the research study database and measure the frequency of counseling by running a clinical reminder report and conducting electronic chart reviews.
3. Determine the impact of the GEM intervention on obesity-related counseling practices and attitudes in primary care providers.
 - a. We will survey providers to measure 5As-related competency and attitudes about weight loss using validated survey items. ¹³ The feasibility and acceptability of the intervention will be evaluated using RE-AIM analysis.

- Participated in MOVE!, DPP, or another intensive weight management program (>4 sessions) in the past year,
- Have a history of bariatric surgery,
- Are pregnant, breastfeeding or become pregnant during the intervention period,
- Have a provider who states they should not participate,
- Have self-reported inability to read at 5th grade level.
- Currently take weight-loss medications or diabetes medication that may impact weight change
- Receive chemotherapy or cancer treatment
- Had metastatic cancer in the last 6 months
- Does not want to lose weight

We are excluding individuals with any of the above listed conditions as this will likely impact their ability to fully participate in this study. Additionally, some of these listed health conditions may limit physical activity. As this intervention includes telephone weight management counseling and reviewing of printed weight management materials, we are excluding participants without a telephone or participants who cannot read material written at the 5th grade level or above.

We will use phone screen and EHR information to verify inclusion and exclusion criteria.

Vulnerable Subjects

No vulnerable populations will be included as part of this weight management intervention study.

III. Methods and Procedures

[figure not shown]
We will conduct a cluster-randomized controlled trial of the GEM intervention at two healthcare systems in New York City: The VA New York Harbor Healthcare System (Manhattan campus) and Montefiore Medical Group (4 sites affiliated with New York City Research and Improvement Networking (NYC RING) practice-based research network. Participants will be randomized at the team level (19 teams with approximately 28 providers and 512 patients to achieve a sample size of 384 patients at 12 month follow-up for the primary outcome assessment). The primary care teams will be randomized using a random number generator (block randomization with block size of four) to either the GEM Intervention or Enhanced Usual Care arms. Randomization will be stratified by healthcare system (MMG and VA).

Intervention Arm – GEM

The GEM intervention leverages the patient-centered medical home model (see Figure 1 below) by using the GEM tool to provide individually tailored, patient-centered care at the time of the primary care visit, promote standardized weight management counseling by health coaches and primary team members, coordinate care between teams and other weight management service providers/programs (e.g., dietitians, health educators, DPP), and provide feedback to the provider and primary care team about patients' weight management-related goals, progress, and care. Patients in the GEM intervention will complete the following (items 1–2 will be completed at the baseline visit). Average times to complete are included below based on pilot testing.

1. Complete the GEM tool (20 minutes)
2. Meet with a health coach and review tailored patient report and educational materials (30 minutes)
3. Meet with their primary care team for regularly scheduled visit (varies 15–45 minutes, 1–8 times/year)
4. Receive 12 telephone coaching calls from health coach (20–30 minutes each)
5. Follow up as needed with primary care teams (varies)

Figure 1: How GEM intervention fits within PCMH

identifies intensive weight management programs and self-monitoring options, allowing patients to choose which to discuss with the health coach and primary care team. This tool also generates an individualized patient report, provides tailored educational materials, and produces a report for the primary care team through the EHR. Although developed initially for the VA, it can be customized for other healthcare systems with minimal programming.

❖ **GEM Tool:** If needed, health coaches will help patients to use the GEM tool. The online program is optimized for use on tablet computers and designed to support health coach and primary care team counseling. It assesses current behaviors, barriers, and facilitators to weight loss via a 16-item questionnaire, provides tailored advice, and guides patients to set weight loss (5–10%)¹⁰, diet, and physical activity (PA) goals. It

❖ **Baseline Health Coach Visit:** After completing the GEM tool, a Health Coach meets with the patient for 30 minutes (based on our pilot study). Sessions will be audio-recorded for fidelity checks and health coach training. The Health Coaches will perform the following tasks:

- Make initial goals into SMART (Specific, Measurable, Attainable, Relevant, Timely) goals⁶³
- Encourage participation (using MI) in MOVE, DPP, or community-based programs/gyms
- Teach how to self-monitor weight, diet, and PA behaviors via pedometer, food log, and/or weight management apps (e.g. MOVE! Coach mobile^{70,71} on iPhones, My Fitness Pal⁷² on Androids)

- Provide brief MI and Brief Action Planning⁷³ to address barriers and increase patient self-efficacy
- Facilitate meetings with extended team members (e.g. health educators, dietitians, primary care physicians) if needed
- Enter a report for primary care teams into EHR from the GEM tool
- Communicate potential barriers/concerns to the team at baseline visit and as needed throughout the intervention period (e.g., via EHR notes, secure messaging system, telephone, and/or team meetings)
- ❖ **Telephone Coaching:** To achieve sufficient intensity according to USPSTF guidelines,¹⁰ we will incorporate 12 telephone coaching calls by a health coach over 12 months. Scheduled calls will occur every 2 weeks (biweekly) for months 1–3, monthly for months 4–6, and every other month (bimonthly) for months 7–12. GEM Intervention arm patients will receive a reminder call or an electronic reminder via MyHealtheVet or VA's Annie texting service to self-monitor their weight, food intake, and PA for at least 3 days prior to the coaching call. Studies suggest that episodes of short, consistent self-monitoring (for 3 days) reduce weight and may improve adherence.⁷⁴ Health coaches will use self-reported self-monitoring data (from pedometers, food logs, and smart phone apps) to determine goal adherence and counsel patients to encourage small changes.⁴⁹ Health coaches will document sessions in REDCap, help patients create new goals when appropriate, and use MI techniques to address barriers to behavior change. Patients will be able to contact health coaches via telephone for additional support. Patients will be reminded to discuss their goals during their next primary care visit (if scheduled).
- ❖ **Provider Role:** Providers in the GEM arm will provide 3–5 minutes of counseling, use clinical reminders to document this counseling, provide brief MI to address barriers (depending on time and patient needs), and discuss GEM-generated weight management goals during future visits. The GEM tool creates a report to communicate data to the participant's primary care team and generates a clinical reminder which facilitates documentation of primary team goal setting conversations and counseling.

Control Arm – Enhanced Usual Care (EUC)

Patients in the EUC arm will receive non-tailored weight management handouts by health coaches (Health Bulletins from the NYC DOHMH).^{79–81} Patients will follow-up with their primary care teams as needed.

Data Collection

Patients: Assessment will occur at the following time points:

- ❖ At Baseline, 6, 12, and 24 months, patients will meet in-person or over the phone (for follow-up) with a research assistant (RA) to complete surveys; measure weight, height, blood pressure, and waist circumference. Baseline surveys will include a pre-survey (completed before receiving GEM Intervention/Enhanced Usual Care). Electronic chart review will also occur at these time points. The RA will administer all surveys and enter the data directly into our REDCap database. To compensate for

travel and time spent completing study measurements, patients will be given \$25 dollars for the baseline study visit, \$30 dollars for the 6-month study visit, \$40 dollars for the 12-month study visit, and \$50 for the follow-up 24-month visit and \$20 dollars for the optional one hour opinion session and 2 follow-up phone calls. During the baseline visit we will encourage patients to sign-up for MyHealtheVet, if they haven't done. In addition, we will inform patients about the VA's secure Annie texting service and help them to sign up, if requested, as another option to receive reminder text messages for appointmentsIf patients are signed-up for MyHealtheVet, they can choose to receive reminders for their upcoming study visits or health coach phone calls electronically via myHealtheVet. Alternatively, patients can choose receive reminder phone calls from secure VA phones lines or via the secure Cisco Jabber application.. Before upcoming phone coaching calls and study visits, we will send reminders via the secure messaging system MyhealtheVet, VA's Annie texting service or make phone calls via secure VA phone lines or via the secure Cisco Jabber application.

- ❖ When performing telephone Coaching Calls (patients in GEM Intervention arm only), Health coaches will use a counseling tool that also facilitates data collection into REDCap database.
- ❖ Chart reviews 12 and 24 months post-baseline visit to explore maintenance of counseling post-intervention

Primary Care Teams: At 12 months, we will give surveys to providers, which will be administered in paper and then entered into our REDCap database. Alternatively, we will administer the provider survey online via REDCap. Furthermore, we will conduct qualitative interviews, and audiotape select visits.

Future Directions: In future versions of the GEM intervention we would like to add a visualization technique called Mental Contrasting with Implementation Intentions (MCII) that is utilized through an exercise called WOOP (Wish, Outcome, Obstacle, Plan). MCII is a novel, practical strategy that was developed and tested through 20+ years of research to promote motivation and behavior change, particularly for challenging behaviors.¹¹⁰⁻¹¹⁵ In order to obtain data on feasibility and acceptability among Veterans without introducing the burden of an additional visit, we will invite up to 20 participants in either arm at the Manhattan VA site to participate in an optional one hour session at their 24 month visit for an additional \$20. Veterans that agree to this additional session will be reconsented with the revised consent form describing this session. During this session they will receive training on WOOP and will be shown how to use the free downloadable WOOP app.²⁴ We will then ask them to share their opinions on WOOP and the app. We will not collect any information from the WOOP app and discussed this piece of the protocol with the Privacy Officers ([name] and [name]). In addition to this training, we will ask each participant a few brief questions related to goal commitment and stage of change before and after the WOOP training. We will also ask permission to follow up via telephone at 3 days and 1 month after the training to see if they have used the technique to make any changes related to weight, diet or physical activity. The materials for this session can be found in Appendix F.

Data Analysis and Data Monitoring

First, all the variables will be summarized (intention-to-treat approach) using mean (with standard deviation) and median (with interquartile range for continuous variables and frequency table for categorical variables) overall and by interventions arms, respectively. Then, Mann-Whitney tests for continuous variables and Fisher's exact tests for categorical variables will be used to check if both providers' and patients' baseline characteristics are balanced between the interventions arms.

Impact of the GEM intervention on weight change, and clinical and behavioral outcomes:

The primary outcome is mean weight loss at 12 months. Mann-Whitney tests for continuous outcomes (e.g., weight loss) and Fisher's exact tests for categorical outcomes (e.g., whether or not patients achieve $\geq 5\%$ weight loss) will be used to compare the two intervention arms at 12 months. Unadjusted confidence intervals will be computed to compare the effects of the GEM intervention on outcomes with the effects of enhanced usual care on outcomes. Moreover, we will use repeated measures modeling, based on mixed models, to compare outcome variables between intervention arms, using all the data at baseline and three follow-up visits. Such modeling can adjust for baseline characteristics (e.g. diabetes, gender), taking into account: a) the correlation among patients within providers, and b) the correlation among repeated measures within patients. Model-based adjusted confidence intervals will be provided to also measure the effects of the intervention on outcomes. Although the repeated measures modeling can address missing data automatically, assuming it is missing at random, we will further use a multiple imputation procedure to conduct sensitivity analyses under the assumption of missing data not at random. The sensitivity analyses will use pattern-mixture models to examine if the statistical findings are robust across several scenarios, including the least-favorable scenario where the missing data from the GEM intervention arm follows the same pattern as that of the observed data from the usual care arm.

Predictors of weight loss in the GEM intervention arm related to: a) goal setting processes and b) intervention components: We will use visualization tools, such as scatterplots and descriptive analyses (e.g., Spearman correlation coefficients) to display the association between weight change and potential predictors. Multivariate regression models will be used to examine the effects of those predictors, which we suspect will be associated with weight loss in the intervention arm. Multivariate linear regression models will be considered for continuous outcomes and multiple logistic regression models will be considered for binary outcomes. Missing data will be dealt with using inverse-probability-weighted methods.

Impact of the GEM Intervention on obesity-related counseling practices and attitudes in primary care providers: We will use Mann-Whitney tests for continuous provider-level outcomes and Fisher's exact tests for categorical provider-level outcomes to compare the two intervention arms at each survey. Confidence intervals of the effects will also be computed.

Data Monitoring: There will be no formal data and safety monitoring board for this

protocol as there is only minimal risk associated with participation in the current study. The PI will monitor data and safety. Should unanticipated reportable events occur, defined as internal or external events (such as deaths, life-threatening experiences, injuries, breaches of confidentiality, or other problems) any time during or after the research study, which in the opinion of the PI are unanticipated, the PI will report them immediately to the NYU IRB. Any new information indicating a change to the risks or potential benefits of the research, any deviation from the protocol, and any possible serious or continued non-compliance will be reported to the NYU IRB by the principal investigator immediately.

Data Storage and Confidentiality

Storage of Subject Data: All subject data collected from the GEM online tool including survey responses and recording of responses while using the tool, interviews, focus groups, pre/post surveys, and measurements will be kept confidential and anonymous through de-identification. This signifies that subject names, dates of birth, and primary care provider names will be de-identified both in audio and written script during the transcription, segmentation, and coding process. Study session data will be entered into REDCap, which is a password-protected database. Subjects will each be given a study identification number, which will be stored in the password-protected database. Patient identifying information (e.g. subject name and date of birth) will be maintained REDCap, which is a password-protected database. All paper data will be kept in a locked, fire-proof file cabinet dedicated to the study that is kept in one of the study team's locked offices (15028BN, 15028AN 15028CN, or 15161N at the Manhattan VA).

Access to Subject Data: Only IRB-approved study personnel, including the Principal Investigator, Co-Investigators, Research Coordinator, and other research staff, will have access to the data for entry and analysis. Healthcare providers who are not key personnel will not be informed of any responses given by subjects during the study visit.

Retention of Subject Data: Subject data will be kept throughout the duration of the study and after the study has concluded to continue with data analysis. When data is no longer needed it will be disposed of appropriately via shredder in order to continue protecting subject confidentiality and anonymity.

IV. Risk/Benefit Assessment

Risk

Any research study has possible risks and discomfort and on a rare occasion, unknown and unforeseeable (unanticipated) risks may also occur. Participation in the study poses no more than minimal risks to the subject's physical and mental health as well as personally identifiable information. Subjects may experience frustration that is often experienced when completing surveys. Some questions may be of a sensitive nature, and subjects may therefore become distressed as a result. If, however, subjects become distressed by a question, subjects have the right to stop at any time or choose not to answer a question or certain questions.

The research team understands that discussing topics related to weight, diet, physical activity, and/or an individual's experiences with these topics can be emotional given the stigma surrounding obesity and its associated medical problems within society.

Protection against Risks

All members of the research team have been extensively trained in order to effectively facilitate conversations and minimize the level of discomfort that individuals may face when dealing with sensitive topics throughout the duration of the study. In addition, any potential behavioral changes related to diet or physical activity will be assessed and approved beforehand by properly trained individuals, which include the Principal Investigator, Co-Investigators, Research Coordinator, and other research staff.

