❖ **Patient Recruitment (Figure 2 below)** – Using the Patients Health Information Systems and Technology Architecture (VistA), the VA's Health Information Technology system, and the Montefiore EPIC and Clinical Looking Glass systems, we will identify patients with upcoming primary care appointments who meet the eligibility criteria. A Research Assistant (RA) will confirm eligibility by EHR and provider review. One to two weeks before their baseline visit, eligible participants will be sent a letter signed by both the Principal Investigator (PI) and giving them the opportunity to opt out (i.e., request to not be contacted). The RA will call patients to recruit, screen for eligibility, and schedule the baseline. This allows enough time for all intervention components to be completed, and is responsive to patient scheduling preferences expressed in a similar recruitment strategy used in the VA PROVE study⁶⁵ and our pilot studies.

Eligibility will be based on the inclusion and exclusion criteria established for the study. Participation in the study is completely voluntary and all prospective subjects may refuse to participate or withdraw from the study at any given time.

Figure 2: Recruitment and Eligibility Screening

Process of Consent

Consent will be obtained by a research assistant trained in consenting protocols. Once subjects have been identified as eligible, the study will be described in detail and informed consent will be obtained from subjects who wish to participate. An audio-video consent form will also be described in detail for subjects who agree to have their study session audio recorded.

Subject Capacity

In order for subjects to be eligible to participate in the study, subjects must have the capacity to give informed consent. Capacity will be assessed with the set of inclusion and exclusion criteria that has been established specifically for this study. In short, participants must be at least 18 years of age, have access to a telephone, be able to travel for in-person evaluations, and not currently have functional impairments that limit

physical activity.

Subject/Representative Comprehension

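### The counseling-maintenance chart review runs on each patient's own clock, so part of its post-intervention window may fall while the same team still has other patients in active GEM

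*Combined protocol and SAP*

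**What the plan says.** Under III. Methods and Procedures, Data Collection, the plan lists "Chart reviews 12 and 24 months post-baseline visit to explore maintenance of counseling post-intervention". The same section schedules patient assessments at baseline, 6, 12 and 24 months and adds "Electronic chart review will also occur at these time points". All of these times count from the individual patient's baseline visit.

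The design and the intervention work at a higher level:

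- Randomization (III. Methods and Procedures): "Participants will be randomized at the team level (19 teams with approximately 28 providers and 512 patients to achieve a sample size of 384 patients".
- Coaching (Telephone Coaching): "we will incorporate 12 telephone coaching calls by a health coach over 12 months", which is a period per patient.
- Provider (Provider Role): "Providers in the GEM arm will provide 3–5 minutes of counseling, use clinical reminders to document this counseling". The GEM tool also "generates a clinical reminder which facilitates documentation of primary team goal setting conversations and counseling".
- Coach-to-team contact (Baseline Health Coach Visit): at baseline, then as needed during an intervention period that is not defined for a team or a provider.
- Entry (section VI, Patient Recruitment): "we will identify patients with upcoming primary care appointments who meet the eligibility criteria".
- Evaluation (Research Design, item b): "We will conduct a RE-AIM (reach, efficacy, adoption, implementation, and maintenance) evaluation of the GEM intervention".

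The documents do not give the length of accrual per team, the date on which a team stops receiving GEM reports or coach contact, or the date on which the reminder is turned off. Data Analysis and Data Monitoring contains no analysis specific to the counseling-maintenance review.

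**The concern.** Maintenance of counseling asks whether providers go on counseling once the support is withdrawn. The plan dates the withdrawal of support from the patient, but a provider sees several study patients who start at different times. A patient who entered early can be in months 12–24 while the same team still receives GEM reports, reminders and coach messages about patients who entered later.

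If being prompted about one patient makes a provider more likely to counsel another, counseling in that stretch is partly supported counseling. The plan would count it as maintained. Without team dates in the abstraction, nobody can later tell the two apart. What is at stake is how the exploratory maintenance result may be read; the primary comparison of 12-month weight loss does not use this measure.

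**Working it through.** **Figures the plan gives.** The sample-size arithmetic reproduces: 384/0.75 = 512. Screening at 20% participation needs 512/0.20 = 2,560, against 2,615 stated, about 2% apart. The plan states no figure for the overlap, so these numbers serve only to set cluster sizes.

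**Cluster sizes.** Patients per team: 512/19 = 26.9. Patients per provider: 512/28 = 18.3. Section VI plans 2–3 providers from each of 19 teams, which is 38–57 rather than about 28; at 57 there are 512/57 = 9.0 patients per provider. I therefore used clusters of 9, 18 and 27.

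**Is entry staggered?** Entry follows each patient's own appointment, and Intervention Arm – GEM expects 1–8 primary care visits a year. Each team must screen about 2,615/19 = 138 eligible patients to enroll about 27. Simultaneous entry is unlikely, but the documents do not say how long entry takes.

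**Overlap model (assumed).** Patients enter uniformly over A months. A patient entering at month t has the window from t+12 to t+24. The team's last patient enters at A and finishes at A+12. The overlap for that patient is min(12, A − t) months. Averaged over t and divided by 12:

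- A ≤ 12: share = A/24
- A > 12: share = [72 + 12(A − 12)]/(12A)

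For example, A = 6 gives 6/24 = 25%, and A = 24 gives (72 + 144)/288 = 75%.

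In a finite cluster the last actual entry falls before A, so the share is lower. Simulation with clusters of 9 to 27 gives the third column. The last column uses a narrower definition of active: only the time when new patients are still having baseline GEM visits, with overlap min(12, max(0, A − t − 12)).

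| Accrual per team, A (assumed) | Share of 12–24 month window before last patient finishes (formula) | Same, clusters of 9–27 (simulated) | Share while baseline GEM visits continue |
|---|---|---|---|
| 0 months | 0% | 0% | 0% |
| 3 months | 12.5% | 10–12% | 0% |
| 6 months | 25% | 20–23% | 0% |
| 12 months | 50% | 40–47% | 0% |
| 18 months | 67% | 56–63% | 8% |
| 24 months | 75% | 64–71% | 25% |

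**From overlap to bias.** Let s be the overlap share, D the fall in the counseling rate once a team's support ends, and c the fraction of that difference that carries over to a finished patient while the provider is still prompted about others. With visits spread evenly over the window, the GEM-arm maintenance rate is overstated by s × c × D. The documents give neither c nor D. At c = 0 the bias is zero whatever the overlap; at c = 1 it is s × D.

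**The case against.** The strongest defense is that the schedule is right for a different question. Reports, reminders and calls are described patient by patient, and coaching ends at 12 months for each one. For the patient whose chart is reviewed, months 12–24 are post-intervention, and asking whether that patient is still counseled is legitimate. The item is exploratory, no test is attached to it, and the plan does not explicitly tie RE-AIM maintenance to this review. Support is also front-loaded: the GEM tool is completed at baseline, calls fall to every other month in months 7–12, and later coach-to-team contact is as needed. On the narrower definition in the last column, the overlap is zero for accrual up to 12 months.

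Much of this stands, and it rules out stronger readings:

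- A reader might infer that a GEM provider remains in the active intervention until the team's last patient finishes. No section says so; it is an inference from the design.
- A reader might infer that much of the window is therefore not post-intervention. That needs accrual of about a year or more per team, and the accrual length is not given.
- A reader might infer that maintenance is overstated. That needs carry-over between a provider's patients, for which the documents offer no figure.
- A reader might infer that late entrants' baseline chart reviews are contaminated and that adjustment for them removes real effect. The plan states no look-back length and specifies no baseline-adjusted comparison of counseling.

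What the defense does not answer is the label. Aim 3 treats counseling as provider practice, and the intervention is meant to change how teams counsel. With no team end date, the data as planned cannot show whether counseling persisted after support ended or persisted because support was still present.

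**Conclusion.** The point holds in a limited form. The maintenance review is timed per patient, the behavior belongs to providers in randomized teams, and staggered entry means the two clocks may disagree. The mean overlap could be anywhere from 0% to about 75% for accrual of 0 to 24 months, under uniform entry and with a team counted as active until its last patient completes 12 months. The resulting bias runs upward from zero and cannot be sized from the documents. The direction (possible overstatement of maintenance) assumes that counseling falls when prompting ends and that prompts carry over between patients. This is a worthwhile, inexpensive repair to an exploratory measure and no threat to the primary outcome.

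**What to change.** 1. Keep the 12- and 24-month patient-anchored chart reviews.
2. For each team in both arms, record the date on which its last enrolled patient reaches month 12. In GEM teams, also record whether the clinical reminder is still on after that date.
3. Flag each abstracted visit as during or after the team's active period, and report counseling by that flag in both arms, so that GEM and Enhanced Usual Care are compared over equivalent periods.
4. Rest any claim that counseling was sustained after support ended on the visits flagged as after. Otherwise describe the measure as counseling after the patient's own intervention period.

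The cost is a few lines of protocol text, one date and one reminder status per team, and a merge into the abstraction file. No patient contact is added. The downside is that fewer visits, mostly from later enrollees, support the stricter claim. In the model above, a patient has no after time within 24 months of baseline if t + 24 ≤ A + 12, that is t ≤ A − 12. At A = 18 this is 6/18, a third of patients; at A = 24 it is 12/24, half. For that reason the visits should be flagged and reported in both groups rather than discarded.
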